Clinical Study Protocol

Drug Substance Dapagliflozin

Study Code DICE study

Edition Number Version 5

Date 27-06-2015

Dapagliflozin on cholesterol metabolism in DM2: dissecting its effect on dyslipidemia by using stable isotope based cholesterol and glucose fluxes; a pilot study

Sponsor:

The following Amendment(s) and Administrative Changes have been made to this protocol since the date of preparation:

Amendment No.	Date of Amendment	Local Amendment No:	Date of Local Amendment
_____	_____	_____	_____
_____	_____	_____	_____

Administrative Change No.	Date of Administrative Change	Local Administrative Change No.	Date of Local Administrative Change
_____	_____	_____	_____
_____	_____	_____	_____
_____	_____	_____	_____

PROTOCOL SYNOPSIS

Dapagliflozin on cholesterol metabolism in DM2: dissecting its effect on dyslipidemia (DICE study)

Principal Investigator

Prof dr [name], internist-endocrinologist AMC-VUMC, Amsterdam, the Netherlands

Study site(s) and number of subjects planned

AMC-VUMC Diabetes Center, 12 DM2 subjects to be included

Study period	Phase of development	
Estimated date of first subject enrolled	Q4 2015	Phase III/IV
Estimated date of last subject enrolled	Q4 2017	Phase III/IV
Dataanalyses and modelling	Q1 2018	

Study design

Single arm intervention trial

Objectives

Primary Objective:	Outcome Measure:
effect of 5 weeks dapagliflozin 10mg on LDL cholesterol in patients with DM2	Change in LDL synthesis

Secondary Objective:	Outcome Measure :

Effect of 5 weeks dapagliflozin 10mg on and Triglyceride cholesterol fluxes
 
Effect of 5 weeks dapagliflozin 10mg on insulin sensitivity and energy expenditure
 
Effect of 5 weeks dapagliflozin 10mg on liver fat content (MRI liver)
	
Change in VLDL secretion and clearance (as determined by $^2\text{H}_3$ Leucine enrichment) and relation to plasma CETP, PLTP and HDL subfractions
 
Change in De novo lipogenesis (as determined by $^2\text{H}_2\text{O}$ deuterated 'heavy' water)
 
oral $1,2,3,4-^{13}\text{C}_{16}$ – palmitate to measure FFA remnant uptake.
 
Change in hepatic and peripheral insulin sensitivity (2 step Hyperinsulinemic normoglycemic clamp with $^2\text{H}_2$ enriched glucose:) and energy expenditure including carbohydrate oxidation and fatty acid oxidation rates in breathing air
 
Change in liverfat MRI spectrum

---	--

Target subject population

Male or postmenopausal female patients with type 2 diabetes BMI > 25 kg/m² and more than 12 weeks a stable dose of metformin treatment > 1500mg (HbA1C \geq 6.5% - <8.5%) FPG<132 mmol/l, LDL cholesterol >2.5 mmol/l, willing to switch to rosuvastatin 10mg once daily for 4 weeks, and then receive 10 mg dapagliflozin once daily orally, for 5 weeks. Measurements (lipid and glucose fluxes) will be done after 4 weeks of rosuvastatin treatment (baseline) and after 5 weeks of dapagliflozin

Duration of treatment

4 weeks of crestor 10mg once daily treatment in all subjects (baseline) and after 5 weeks of dapagliflozin (n=12 DM2 subjects)

Investigational product, dosage and mode of administration

Crestor 10 mg once daily for in total 9 weeks orally

Dapagliflozin 10mg once daily for 5 weeks orally

Statistical methods

All data will be analysed using SPSS for Windows, version 20.0 (SPSS Inc. Chicago, Illinois, USA). Multivariate analysis and ANOVA for repeated measures will be used. Wilcoxon's signed-rank test will be used to compare results between the study groups. -Data will be expressed as median and range.

	PAGE
TABLE OF CONTENTS	
TITLE PAGE	1
PROTOCOL SYNOPSIS.....	2
TABLE OF CONTENTS.....	5
LIST OF ABBREVIATIONS AND DEFINITION OF TERMS	9
1. INTRODUCTION	10
1.1 Background and rationale for conducting this study	10
1.2 Rationale for study design, doses and control groups.....	10
1.3 Study Design.....	12
2. STUDY OBJECTIVES.....	16
2.1 Primary objective	16
2.2 Secondary objectives	Fout! Bladwijzer niet gedefinieerd.
2.3 Safety objectives	16
2.4 Exploratory objectives	17
3. SUBJECT SELECTION, ENROLMENT, RANDOMISATION, RESTRICTIONS, DISCONTINUATION AND WITHDRAWAL.....	17
3.1 Inclusion criteria	17
3.2 Exclusion criteria	17
3.3 Subject enrolment and randomization	17
3.4 Procedures for handling incorrectly enrolled or randomized subjects.....	17
3.5 Methods for assigning treatment groups.....	18
3.6 Methods for ensuring blinding.....	18
3.7 Methods for unblinding.....	18
3.8 Restrictions	18
3.9 Discontinuation of investigational product.....	18
3.9.1 Procedures for discontinuation of a subject from investigational product	18
3.10 Criteria for withdrawal.....	18
3.10.1 Screen failures.....	18
3.10.2 Withdrawal of the informed consent.....	18
3.11 Discontinuation of the study	18

4.	STUDY PLAN AND TIMING OF PROCEDURES.....	18
4.1	Enrolment/screening period	21
4.2	Treatment period.....	21
4.3	Follow-up period.....	21
5.	STUDY ASSESSMENTS	21

Appendix A Signatures

Appendix B Additional Safety Information

<<Appendix C>> <<IATA 6.2 Guidance document>>

<<Appendix D>><<Pharmacogenetics Research>>

<<Appendix X>> <<Other>>

LIST OF ABBREVIATIONS AND DEFINITION OF TERMS

<>>

The following abbreviations and special terms are used in this study Clinical Study Protocol.

Abbreviation or special term	Explanation
AE	Adverse event
CRF	Case Report Form (electronic/paper)
CSA	Clinical Study Agreement
CSR	Clinical Study Report
CTCAE	Common Terminology Criteria for Adverse Event
DAE	Discontinuation of Investigational Product due to Adverse Event
DNA	Deoxyribonucleic acid
EC	Ethics Committee, synonymous to Institutional Review Board (IRB) and Independent Ethics Committee (IEC)
GCP	Good Clinical Practice
ICH	International Conference on Harmonisation
IP	Investigational Product
IVRS	Interactive Voice Response System
IWRS	Interactive Web Response System
LSLV	Last Subject Last Visit
OAE	Other Significant Adverse Event
PGx	Pharmacogenetic research
PI	Principal Investigator
SAE	Serious adverse event
WBDC	Web Based Data Capture

1. INTRODUCTION

1.1 Background and rationale for conducting this study

There is a worldwide epidemic of obesity, which is a major risk factor for the development of common medical conditions such as type 2 diabetes (T2D), dyslipidemia and cardiovascular disease (CVD). Obesity and T2D are leading causes of morbidity and mortality in developed nations with an estimated cost exceeding 400 billion euro in the last 5 years and an estimated 250,000 deaths per year (1). The prevalence of obesity and T2D continues to rise: one out of three adults is expected to be diagnosed with T2D in 2050 (2). Current therapeutic regimens only minimally reduce T2D-related complications and lead to a shift from myocardial infarction to peripheral artery disease and kidney failure. Additionally, all-cause morbidity and mortality is still 10-fold higher in T2D patients compared to healthy subjects (3). This collectively represents a growing unmet clinical need.

In this regard, SGLT2 inhibitors improve glycemic control and are currently investigated in large cardiovascular outcome trials in patients with type 2 diabetes mellitus (4). It has been suggested that the beneficial cardiovascular effects are driven by both improved peripheral insulin sensitivity (5,6) in conjunction with reduced bloodpressure and bodyweight in subjects with type 2 diabetes mellitus, the latter most likely driven by an osmotic (plasmacontraction) effect due to the increased glycosuria (7,8). However a potential disadvantage of all SGLT2 inhibitors might be the adverse effect seen on fasting lipid profiles including decreased HDL cholesterol and increased LDL-cholesterol and triglyceride plasma levels (9,10,11). In this regard ,there is a striking similarity with the observation of increased APOB synthesis due to plasma contraction in patients with nephrotic syndrome (12). Other mechanisms that might drive the observed dyslipidemic plasma cholesterol profile might include decreased hepatic LDL cholesterol clearance as well as deleterious effects of Cholesteryl ester transfer protein (CETP) resulting altered HDL cholesterol plasma levels. Epidemiological studies have unequivocally shown that high TG and low HDL-C represent strong independent risk factors of CVD. (13) Emerging evidence suggests that TG and HDL lipoproteins are strong interrelated biological parameters and linked to glucose homeostasis. Circulating triglycerides in part derive from VLDL-secretion from the liver as well as from Free Fatty Acid (FFA) uptake in the small intestine, a metabolic flux that is highly regulated by insulin (14). In obese insulin resistant subjects, insulin-mediated suppression of VLDL-synthesis and secretion is reduced resulting in high plasma TG and TG accumulation in the liver (15). Finally, SGLT2 is widely expressed through the human body including in the small intestine (near GLP1 producing L cells) and in the liver (16). Thus suggesting that SGLT2 inhibitors can also affect glucose and lipid uptake in the gut.

We thus propose to further dissect the underlying mechanisms regarding dyslipidemic effects of SGLT2 inhibitors in relation to insulin sensitivity and energy metabolism in uncomplicated DM2 patients. This will be done using previously published stable isotope based techniques to study VLDL, LDL and HDL synthesis (15) as well as for determination of hepatic and

peripheral insulin sensitivity (5). All of these stable isotopes are GMP produced and analyses techniques have been previously used and published by our group (17, 18 and 19).

1.2 Rationale for study design, doses and control groups

Study Hypothesis and rationale

Dapagliflozin 10mg once daily for 5 weeks increases hepatic LDL and VLDL secretion driven by altered CETP in DM2 patients on stable statin therapy (10mg rosuvastatin once daily)

Study design:

Male or postmenopausal female patients with type 2 diabetes (BMI > 25 kg/m² and more than 12 weeks a stable daily dose of metformin treatment > 1500mg) with good glycemic control (HbA1C \geq 6.5% - < 8.5% and fasting plasma glucose < 132 mmol/l) and on stable statin regimen and willing to switch to crestor 5 mg once daily during the study. After 4 weeks of rosuvastatin treatment (20), baseline measurements for glucose and lipid fluxes will be performed and thereafter DM2 patients will be randomized to receive 10 mg dapagliflozin (n=12) orally with rosuvastatin 10mg once daily. Measurements (lipid and glucosefluxes) will be repeated after 5 weeks of dapagliflozin treatment.

Sample size

Previous studies have reported a 10 % increase in fasting plasma LDL plasma levels upon dapagliflozin 10mg once daily treatment in DM2 patients on statin therapy (20). As it can be expected that metabolic effects of SGLT2 inhibition stabilize after 4 weeks (5,6) and lipid fluxes upon intervention are usually determined upon 4-5 weeks after start of intervention (21), we suggest to treat for 5 weeks. A reduction was seen in 8 DM2 subjects of plasma LDL (from 3.1 ± 0.8 to 1.5 ± 0.4 mmol/l) on rosuvastatin treatment, that corresponded with a similar decrease in LDL- ApoB poolsize /synthesis (2.8 ± 0.4 to 1.5 ± 0.4 gram/day, see ref 22). We thus expect 10% higher plasma LDL level (from 3.1 ± 0.8 to 1.7 ± 0.4 mmol/l) with concomitant less decrease in LDL- ApoB poolsize /synthesis (1.8 ± 0.4 gram/day) upon rosuvastatin combined with dapagliflozin 10mg treatment in DM2. Using single sided test (with alfa of 0.05 and 85% power) and using difference in LDL-apoB synthesis of 0.3 gram/day with SD of 0.4, the sample size needs to be 11 DM2 subjects, on dapagliflozin 10mg treatment. Taking a 10% patient dropout rate, we aim to include 12 DM2 subjects in total.

Benefit/risk and ethical assessment

Both rosuvastatin and dapagliflozin have been approved by FDA/EMEA and are widely prescribed. The effect of rosuvastatin alone on lipidfluxes in this group of DM2 patients has already been established (22) which thus allows us to study the mere effect of SGLT2 on

lipidfluxes in DM2 patients on stable statin therapy in a single arm trial. The use of stable isotope infusion is not associated with adverse events. Thus, the risk for patients to participate in this study is minimal.

1.3

Study Design

[figure not shown]

Figure 1

Study day 1: Assessment of cholesterol fluxes

VLDL, LDL, HDL kinetics: Subjects will drink $^2\text{H}_2\text{O}$ (2g per kg body weight), in the evening before the study day. First a blood sample will be drawn for determination of background enrichments. The subjects will sip the deuterated water between 18.00 and 22.00h. Thereafter, they are allowed to drink deuterated water (0.5% enriched) only to prevent dilution of the isotopic label.

The next day, subjects will be admitted to the metabolic unit at 7.30 AM after a 10 hour overnight fast. A catheter will be inserted into an antecubital vein for infusion of the stable isotope tracers. Another catheter will be inserted into a contralateral hand vein and kept in a thermo-regulated (60 C) plexiglas box for sampling of arterialized venous blood. Saline will be infused as NaCl 0.9% at a rate of 50 mL/h to keep the catheter patent. At T=0 (8.00 AM) a bolus of 7mg/kg of L[5.5.5-²H3]-leucine(99% enriched; Cambridge isotopes, Andover, USA) and simultaneously a [1,1,2,3,3-²H5] glycerol (99% enriched; Cambridge isotopes, Andover, USA) bolus of 500mg will be given. (23,24)

At T=0:02,0:04,0:06,0:08,0:10,0:12,0:15,0:20,0:30,0:45, 1,2,3, 4, 6, 8, 10 and 12h blood samples will be drawn for the determination of [2H3] leucine concentration in plasma. For the measurement of [2H3]-leucine and [2H5] glycerol in VLDL, LDL and HDL, blood samples will be drawn at T=-0.30, 0:30, 0:45, 1, 1:15, 1:30, 2, 2:30, 3, 4, 5, 6, 7, 8, 10, and 12h. In addition, at the above time-points blood samples will be drawn for measurement of plasma cholesterol, cholestryl esters, FFA, apoB, apoAI and glycerol. At T=0, 4, 8 and 12h the particle composition and Apo-B mass of the VLDL and LDL fractions will be determined and the apoAI composition of HDL. See the study outline shown in figure 2.

At T=2.00 subjects will be served an oral fat load containing the dietary triglyceride tracer 1,2,3,4-13C16 – palmitate (1-2 grams). The meal will consist of bread, butter, cheese, low fat milk and tea or coffee (63 grams carbohydrates, 56 grams fat (P/S ratio 0.11) and 35.9 grams protein). Blood samples are drawn up to 8 hours after the meal (see figure 2).

During the test only deuterated water will be served ad libitum and the subjects will remain physically inactive. After the last blood sample at T=12h patients will be offered a meal. Time series data from enrichments of plasma leucine, leucine in apoB100 from VLDL and LDL and glycerol in VLDL and LDL are used as input to the kinetic model together with pool size measurements to simultaneously determine the kinetics of VLDL-TG and apo-B100 and LDL apoB and cholesterol. (23,24).

[figure not shown]

Figure 2: study design VLDL-HDL kinetics and visit 2 and 5.

Study day 2:

Assessment of glucose metabolism and lipolysis during a 2-step hyperinsulinemic euglycemic clamp

The clamp will be performed after an overnight fast. A catheter will be inserted into an antecubital vein for infusion of the stable isotope tracers (19). Another catheter will be inserted retrogradely into a contra lateral hand vein and kept in a thermo-regulated (60°C) plexiglas box for sampling of arterialized venous blood. Saline will be infused as NaCl 0.9% at a rate of 50 mL/h to keep the catheter patent. [6,6-2H2] glucose will be used as a glucose tracer (>99% enriched; Cambridge Isotopes, Andover, USA) to study total glucose production and insulin sensitivity. [1,1,2,3,3-2H5]-glycerol (>99% enriched; Cambridge Isotopes, Andover, USA) will be used to study glycerol turnover (as a measure of total triglyceride hydrolysis/lipolysis).

At $T = -2$, blood samples will be drawn for determination of the background enrichments and primed continuous infusions will be started: [6,6-2H2] glucose (prime = 100 minutes of continuous infusion; continuous, $0.11 \mu\text{mol}/\text{kg}\cdot\text{min}$); [1,1,2,3,3-2H5]- glycerol (prime, 1.6 $\mu\text{mol}/\text{kg}$; continuous, $0.11 \mu\text{mol}/\text{kg}\cdot\text{min}$) and continued until the end of the study. At $T=0$, blood samples will be drawn for the determination of enrichments of glucose and glycerol 3 times with a 5 min interval. In addition, blood samples will be drawn for measurements of glucoregulatory hormones, free fatty acids (FFA), inflammatory markers and adipokines.

Resting energy expenditure (REE) will be measured during the final 20 minutes of these 2 hours and during the final 20 minutes of the study day. This will be done by indirect calorimetry. Oxygen consumption and CO₂ production will be measured using a ventilated hood system. These measurements are then used to calculate REE and the respiratory quotient. At T=0:15, infusion of insulin (20mU/m²·min; Actrapid 100 IU/ml; Novo Nordisk Farma B.V., Alphen aan den Rijn, the Netherlands) and glucose 20% (to maintain a plasma glucose level of 5 mmol/L) will be started. [6,6-2H₂] glucose will be added to the 20% glucose solution to achieve glucose enrichments of 1% to approximate the values for enrichment reached in plasma and thereby minimizing changes in isotopic enrichment due to changes in the infusion rate of exogenous glucose. Plasma glucose levels will be measured every 10 minutes at the bedside. At T=2:15, 5 blood samples with an interval of 5 minutes will be drawn to determine glucose enrichments, glucoregulatory hormones, free fatty acids (FFA). At T=2:35 the insulin infusion will be increased (60mU/m²·min; Actrapid 100 IU/ml; Novo Nordisk Farma B.V., Alphen aan den Rijn, the Netherlands). Plasma glucose levels will be measured every 10 minutes at the bedside. At T=4:35, 5 blood samples with an interval of 5 minutes will be drawn for measurements of above mentioned parameters. At T= 4:55 insulin and the isotope tracers will be stopped and patients will be offered a bread meal. The glucose infusion will be tapered down to avoid hypoglycaemia. The stable glucose isotope ([6,6-2H₂]glucose) will be obtained at the hospital pharmacy (AMC) and prepared for infusion by the coordinating investigator (19).

MRI based Quantification of intrahepatic triglycerides (IHTG)

IHTG will be quantified by ¹H-MRS on study day 2 before the clamp procedure. ¹H- MRS spectra will be acquired using a 1.0T Tesla open MRI (25). During the measurements, participants remain in the supine position within the MRI scanner. IHTG content will be obtained using single-voxel ¹H-MRS, using a body array coil as the transmitter and phased surface coils as receivers. MRS measurements will be acquired during breath-hold, using single-voxel stimulated acquisition mode. Volumes of interest in the liver will be located away from major vascular structures and bile ducts. The water and fat resonance peaks, located at 4.65 and 1.3 ppm, will be integrated using jMRUI software and relative fat content will be expressed as the ratio of the fat peak area over the cumulative water and fat peak areas. Calculated peak areas of water and fat will be corrected for T₂ relaxation (T₂water, 34 ms, T₂fat, 68 ms) and the percentage hepatic fat content will be calculated. The measurements will take approximately 30 minutes.

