2. STUDY OBJECTIVES

Primary objective Objectives

Primary Objective:	Outcome Measure:
effect of 5 weeks dapagliflozin 10mg on LDL cholesterol in patients with DM2	Change in LDL synthesis

Secondary Objective:	Outcome Measure :
Effect of 5 weeks dapagliflozin 10mg on and Triglyceride cholesterol fluxes	Change in VLDL secretion and clearance (as determined by ² H ₃ Leucine enrichment) and relation to plasma CETP, PLTP and HDL subfractions Change in De novo lipogenesis (as determined by ² H ₂ O deuterated 'heavy' water) oral 1,2,3,4- ¹³ C ₁₆ – palmitate to measure FFA remnant uptake.
Effect of 5 weeks dapagliflozin 10mg on insulin sensitivity and energy expenditure	Change in hepatic and peripheral insulin sensitivity (2 step Hyperinsulinemic normoglycemic clamp with ² H ₂ enriched glucose:) and energy expenditure including carbohydrate oxidation and fatty acid oxidation rates in breathing air
Effect of 5 weeks dapagliflozin 10mg on liver fat content (MRI liver)	Change in liverfat MRI spectrum

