3.2 Exclusion criteria

History of cardiovascular event

Smoking

Creatinin clearance < 60ml/min

Alcohol abuse (>4 units/day)

AST or ALT elevation (>2.5x upper limit)

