4. STUDY PLAN AND TIMING OF PROCEDURES

Clinical Study Protocol
 Drug Substance Dapagliflozin
 Study Code DICE study
 Edition Version 5
 Date 28-02-2015

Table 1 Study Plan DICE study detailing the procedures

Visit	1	2	3	4	5	6	For details see Protocol Section
Week	0	0	2.5	5	5		
Day	-						
Written informed consent (including tissue samples)	X						
Demographics	X						
Physical examination, height and weight	X			X		X	
Medical/surgical history/ECG	X						
Inclusion/exclusion criteria	X						
Fluxes and MRI		X	X		X	X	
Vital signs	X	X	X	X	X	X	
Start study treatment			X				
Treatment dispensed/returned	X	X				X	
Concomitant medication	X	X	X	X	X	X	

Visit	1	2	3	4	5	6	For details see Protocol Section
Visit window	Screening and start rosuvastatin						
Days -28 to 0 for Visit 1							
7 ±1 day for Visit 2& 3							
7 ±1 day for Visits 4							
7 ±1 day for Visit 5&6							
Week	0	0	2.5	5	5		
Day	-						
Adverse event review (AEs and SAEs)		X	X	X	X	X	
Blood samples for haematology and clinical chemistry	X	X	X	X	X	X	
24h Urinalysis		X	X		X	X	

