8.3.1 Efficacy analysis set

Effect dapagliflozin on HDL catabolic fractional rate and plasma CETP levels

Effect dapagliflozin on triglyceride/VLDL synthesis rate and liver fat MRI signal

Effect dapagliflozin on hepatic and peripheral insulin sensitivity

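### The clamp has no defined index for peripheral insulin sensitivity and no clamp-timed urine; if the index is absolute glucose disposal, urinary glucose on dapagliflozin is counted as tissue uptake

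*Combined protocol and SAP*

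**What the plan says.** Section 2 lists as a secondary outcome "Change in hepatic and peripheral insulin sensitivity", measured by a two-step clamp. Section 8.3.1 repeats it as "Effect dapagliflozin on hepatic and peripheral insulin sensitivity". Neither gives an index or a formula.

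Section 1.3, Study day 2, describes the procedure. Labelled glucose is infused "to study total glucose production and insulin sensitivity". Insulin runs at 20 mU/m²·min from T=0:15 and at 60 mU/m²·min from T=2:35 until T=4:55. A 20% glucose infusion is adjusted "to maintain a plasma glucose level of 5 mmol/L". Enrichment is sampled at T=0, from T=2:15 and from T=4:35. All samples described are blood; the only other measurement during the procedure is indirect calorimetry.

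Section 1.1 attributes part of the drug class's action to an osmotic "effect due to the increased glycosuria".

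Table 1 in section 4 has a row "24h Urinalysis" at Visits 2, 3, 5 and 6, the same visits as the flux measurements. The caption of Figure 2 assigns the lipid kinetics to Visits 2 and 5, which leaves Visits 3 and 6 for the clamp. The only urine glucose test named is the dipstick in section 5.2.1. Section 8.5.2 gives general-purpose tests, and section 8.5.5 plans no sensitivity analysis.

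**The concern.** A glucose tracer measures everything that leaves plasma. It does not separate uptake by tissue from loss into urine. Before dapagliflozin, loss at a plasma glucose of 5 mmol/L can be taken as close to nil (an assumption; the documents do not state it). On the drug it continues during the clamp. If absolute disposal is reported as peripheral sensitivity, the second visit therefore carries a component that the first does not, and some of the apparent change is renal.

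Section 1.1 anticipates improved peripheral insulin sensitivity with this class, so an upward artefact could pass as confirmation. Urine timed to the clamp steps cannot be recovered after the visit, so this has to be settled in the protocol and not at analysis.

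**Working it through.** The plan states no expected disposal, urinary excretion or effect size for this outcome, so there is no figure of its own to reproduce.

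**Inputs from the documents.** Plasma glucose during the clamp is 5 mmol/L. Patients with "Creatinin clearance < 60ml/min" are excluded (section 3.2), so filtration is taken as at least 60 ml/min.

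**Assumed inputs.** Filtration up to 120 ml/min; 20 to 50% of filtered glucose excreted on the drug and about none before it; body weight 90 kg; true tissue uptake 20 to 40 µmol/kg/min.

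**Mass balance at steady state**

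- Tracer disposal = tissue uptake + urinary excretion
- Urinary excretion = filtration × plasma glucose × excreted fraction / weight
- Apparent change with tissue uptake unchanged = urinary excretion / tissue uptake

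**Absolute disposal**

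- Filtered load: 60 × 5 = 300 to 120 × 5 = 600 µmol/min.
- Excretion: 300 × 0.20 / 90 = 0.67 to 600 × 0.50 / 90 = 3.33 µmol/kg/min.
- Apparent rise: 0.67 / 40 = 1.7% to 3.33 / 20 = 16.7%.
- Mid case at 90 ml/min, 35%, 90 kg, uptake 30: 450 × 0.35 / 90 = 1.75, and 1.75 / 30 = 5.8%.
- Mid case at 90 ml/min, 35%, 80 kg, uptake 25: 450 × 0.35 / 80 = 1.97, and 1.97 / 25 = 7.9%.
- Wider assumptions (80 to 100 kg, uptake 15 to 40): excretion is 0.60 to 3.75 µmol/kg/min and the apparent rise is 0.60 / 40 = 1.5% to 3.75 / 15 = 25%.

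The relative error is larger where disposal is lower, as at the first insulin step.

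**Other indices the wording would allow**

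- Percent rise over the T=0 value: on the drug, the basal value contains urinary loss too. With assumed uptake rising from 12 to 30, the true rise is 18 / 12 = 150%. Adding a loss of 2 to both gives 14 to 32, and 18 / 14 = 129%. The bias is downward.
- Difference between the two insulin steps: both target 5 mmol/L, so a similar loss in each largely cancels.
- Glucose infusion rate: this equals tissue uptake plus urinary loss minus endogenous production. A drug-related rise in endogenous production, which the title of reference 5 reports, would offset part of the loss.

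**Could the 24h urine serve as the correction?** If mean glucose over the day is 8 to 10 mmol/L (assumed) and excretion follows filtered load, a 24h rate would exceed the clamp rate by 8 / 5 = 1.6 to 10 / 5 = 2.0 times and would over-correct by that factor.

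**The case against.** The strongest reply is that the index is undefined, so no direction can be asserted. That stands: the upward bias belongs to absolute disposal only. A reader might infer that the error always favours the drug, and the working above shows that it need not.

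Second, Table 1 schedules a 24h urine at exactly the flux visits, in its own row, which is compatible with an intended correction. This stands in part. Its analytes, start and stop times and use are not stated, so one cannot say that no correction was intended. But nothing links the collection to the clamp, and an undivided total cannot give the loss at 5 mmol/L.

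Third, nearly all the size is assumed. Only 5 mmol/L and 60 ml/min come from the plan, the top of the range needs every extreme at once, and the bottom is under 2%. This also stands. A reader might infer that the secondary result would be wrong or uninterpretable; a mid-case error of 6 to 8% on a secondary outcome of a pilot study does not support that.

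Finally, a reader might blame the single-arm design and suppose that a control group would remove the bias. It would not. The loss is specific to the drug, so a comparison with placebo would contain all of it.

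**Conclusion.** The point holds in conditional form. The plan neither defines its index of peripheral insulin sensitivity nor provides for urinary glucose during the clamp, although it describes the glycosuria. If absolute tracer disposal is used, the before/after change is biased upward by roughly 2 to 17%, with mid cases of about 6 to 8%. Those percentages rest on the assumed upper filtration rate, excreted fraction, weight and tissue uptake, and on negligible loss before the drug. Under other indices the bias may shrink, be partly masked or reverse. The change is worth making because it is cheap and the measurement cannot be obtained later.

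**What to change.** At Visits 3 and 6, divide the planned 24h collection so that the clamp steps are separate portions: a void just before insulin starts (T=0:15), then at T=2:35 and T=4:55. Each portion covers 140 minutes. Record volume, measure glucose quantitatively, and compute excretion as volume × concentration / 140 min / body weight.

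In section 8.5.2, define peripheral insulin sensitivity as tracer glucose disposal minus the urinary glucose excretion rate of the same step, at both visits, and report uncorrected values alongside. In section 4, state the analytes, timing and use of the 24h urine.

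The cost is three timed voids within each existing visit, 12 patients × 2 visits × 2 steps = 48 urine glucose assays, and a few sentences of text. There are small downsides. Incomplete voiding adds noise, and a mid-clamp void is awkward with both arms cannulated. The first portion also includes the fall from fasting glucose to 5 mmol/L, while enrichment is sampled only from T=2:15 to the end of that step, so the step-1 correction may be slightly too large. Step 2 is the cleaner estimate.
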